6.4 Subject Enrollment

Before subjects begin participation in any study-specific activities/procedures, Amgen requires a copy of the site's written institutional review board/independent ethics

committee (IRB/IEC) approval of the protocol, informed consent form, and all other subject information as applicable (see Section [12.3](#)).

The subject must personally sign and date the IRB/IEC and Amgen approved informed consent before commencement of study-specific procedures.

A subject is considered enrolled when the investigator decides and all eligibility criteria (from screening visit and baseline/day 1 visit) are met. The investigator is to document this decision and date, in the subject's medical record and in the enrollment case report form (CRF). At baseline/day 1 visit, if the subject meets all eligibility criteria, he/she is subsequently enrolled and randomized to a treatment regimen. Subjects who meet screening visit eligibility but do not meet baseline/day 1 visit eligibility criteria are considered screen fails. Subjects may rescreen up to 2 times, as described in Section [9.1.1](#).

Each subject who enters into the screening period for the study (defined as the point at which the subject signs the informed consent form) receives a unique subject identification number before any study-related activities/procedures are performed. The subject identification number will be assigned by IRT. This number will be used to identify the subject throughout the clinical study and must be used on all study documentation related to that subject.

The subject identification number must remain constant throughout the entire clinical study; it must not be changed after initial assignment, including if a subject is rescreened. This number will not necessarily be the same as the randomization number assigned for the study.

6.5 Screen Failures

Screen failures are defined as subjects who consent to participate in the clinical study but are not subsequently enrolled in the study. A minimal set of screen failure information will be collected that includes demography, screen failure details, eligibility criteria, and any serious adverse events.

Individuals who do not meet the criteria for participation in this study (screen failure) may be rescreened up to 2 additional times. Refer to Section [9.1.1](#).

7. Treatments

Investigational product is defined as any investigational product(s), non-investigational product(s), placebo, or medical device(s) intended to be administered to a study subject according to the study protocol.

Note that in several countries, investigational product and non-investigational product are referred to as investigational medicinal product and non-investigational medicinal product, respectively.

The Investigational Product Instruction Manual (IPIM), a document external to this protocol, contains detailed information regarding the storage, preparation, destruction, and administration of each treatment shown in Section 7.1.1 below.

7.1 Treatment Procedures

7.1.1 Investigational Products

AMG 570 will be manufactured and packaged by Amgen Inc. and distributed using Amgen clinical investigational product distribution procedures. AMG 570 is a clear colorless sterile solution which will be packaged in open-label 5 mL glass vials containing 70 mg/ml of AMG 570 formulated with [REDACTED]

[REDACTED] Placebo will be presented in identical containers and stored/packaged the same as AMG 570, but will not contain AMG 570 protein. All AMG 570 and placebo will be shipped to the study site and should be stored the same as AMG 570 at 2°C to 8°C with limited exposure to light.

For more information regarding investigational product handling and preparation please see the study-specific IPIM which is provided as a separate document.

Table 7-1. Investigational Products

Investigational Product Name	Amgen Investigational Product: AMG 570 ^a	Placebo
Dosage Formulation	Clear colorless sterile solution in 5 mL glass vials containing 70 mg/mL of AMG 570	Placebo will be presented in identical containers, and stored/packaged the same as AMG 570
Unit Dose Strength(s)/ Dosage Level(s) and Dosage Frequency	70 mg/Q2W 280 mg/Q2W 420 mg/Q2W	
Route of Administration	SC injection	
Accountability	Total volume of preparation, quantity administered start date, start time, and box number of AMG 570 is to be recorded on each subject's CRF.	
Dosing Instructions	PI or designee will administer product in subject's abdomen. Dosing must be administered on day of scheduled visit after all clinical assessments have been completed. No dose adjustments for weight or restrictions with food intake are required.	

CRF = Case Report Form; PI = Principal Investigator; SC = subcutaneous; Q2W = every 2 weeks

^aAMG 570 will be manufactured and packaged by Amgen and distributed using Amgen clinical investigational product distribution procedures.

7.1.2 Non-investigational Products

No non-investigational products will be used.

7.1.3 Medical Devices

There are no investigational medical devices used in this study.

Non-investigational medical devices may be used in the conduct of this study as part of standard care.

Non-investigational, non-Amgen medical devices (eg, syringes, sterile needles), that are commercially available are not usually provided or reimbursed by Amgen (except, for example, if required by local regulation). The investigator will be responsible for obtaining supplies of these devices.

7.1.4 Other Therapies

7.1.4.1 Immunosuppressants/Immunomodulators

Subjects should receive stable doses of immunomodulators and/or immunosuppressants agents from \geq 8 weeks prior to screening through week 52. If a subject requires a higher dose of an immunosuppressant/immunomodulator or requires a new immunosuppressant/immunomodulator at any time during the study period (other than CS, see below), the subject may continue the study but will be considered treatment **failures for primary efficacy endpoint analyses for the subsequent time points. These subjects will also be allowed to continue investigational product at the investigator's discretion, except subjects who initiate any immunosuppressant/immunomodulator listed in Section 7.1.7 (treatments a through i).**

Subjects may reduce dosage in immunomodulators and/or immunosuppressants if the subject develops unacceptable side effects or abnormal laboratory values attributable to these medications.

7.1.4.2 Oral, Intramuscular, and Intravenous Corticosteroids

Initiation or temporary increases in the OCS dosage are not encouraged but are allowed if initiated at any time between weeks 0 to 8 with a return to baseline dose within the subsequent 2 weeks. In such cases, initiation or temporary increase of OCS is limited to a dose \leq 5 mg/day of prednisone (or equivalent). Subjects who require higher dose **increase of OCS (> 5 mg/day of prednisone or equivalent), or IM CS or IV CS, or those who** cannot return to baseline dose within the following 2 weeks or subjects who require initiation or CS dose increase at any time point after week 10 can continue the study **or**

investigational product at the investigator's discretion but will be considered treatment failures for the primary efficacy endpoint.

Subjects may begin tapering OCS up to the week 44 assessment with initiation of tapering based upon clinical judgment of the treating physician. The tapering schedule should be directed at the discretion of the investigator but should generally not be tapered more than 10% to 20% of the prior dose per week. Between weeks 44 and 52, the OCS dosing should again remain stable.

7.1.4.3 Topical Corticosteroids and Topical Calcineurin Inhibitors

Subjects who are using topical **CS** or topical calcineurin inhibitors must remain on a stable regimen but may discontinue topical corticosteroids at any time if clinically indicated.

7.1.4.4 Non-steroidal Anti-inflammatory Drugs (NSAIDs) and Other Analgesic Therapies

Subjects taking non-steroidal anti-inflammatory drugs (NSAIDs) or other analgesic therapies should remain on stable dose from day 1 through week 52. NSAIDs or other analgesic therapies used for SLE disease activity should be held for 24 hours prior to the scheduled monthly efficacy assessments. Subjects can return to their regular doses immediately after the clinical visit is complete. Discontinuation or reduction of NSAIDs or other analgesic therapy dose during the study is allowed based on the investigator's judgment. Initiation or increases in the NSAIDs or other analgesic therapy dose during the study are allowed if: 1) not initiated within 24 hours of the scheduled monthly efficacy assessments, 2) the subject returns to baseline dose within the subsequent 2 weeks, and 3) it is not within 2 weeks prior to the week 52 visit.

7.1.4.5 Anti-proteinuria Agents

Subjects with SLE-related proteinuria taking anti-proteinuria agents (eg, angiotensin II receptor blockers, angiotensin-converting enzyme inhibitors), should remain on stable dose through week 52. Discontinuation or dose reduction of anti-proteinuria agents during the study is allowed in case of intolerance or toxicity. Initiation or dose increase of anti-proteinuria agents (eg, angiotensin II receptor blockers, angiotensin-converting enzyme inhibitors) for the purpose of SLE-related proteinuria during the study should be avoided.

7.1.5 Other Treatment Procedures

7.1.5.1 Home Health Care Visits

Section 7.1.5.1 is not applicable for participating sites in Bulgaria.

If permitted by national and/or local regulations, the investigator may utilize a qualified home health care service provider, selected and approved by the sponsor, for investigational product administration. This service can be offered to subjects that have not experienced adverse events considered to be related to investigational product that in the opinion of the investigator may pose a risk for home health care administration of investigational product. The study may include up to 8 home visits, including weeks 22, 26, 30, 34, 38, 42, 46, and 50. [REDACTED]

[REDACTED] . In addition to administration of investigational product, safety assessments including vital signs, adverse events, serious adverse events, and concomitant medications review will be collected.

Home health care staff must be included on the study delegation log (authorized by the investigator) before any study-related tasks to be conducted by each home health care provider are started. In addition, study-specific training including requirements for recording source documentation for the home health care provider, must be completed before they conduct any study-related tasks.

Following home health care visit, all the information collected will be documented on the home health care services visit worksheet and forwarded to the investigator.

A comprehensive list of all home health care services, as well as mandatory procedural and data collection requirements, will be separately provided in a home health care manual.

7.1.6 Product Complaints

A product complaint is any written, electronic, or oral communication that alleges deficiencies related to the identity, quality, durability, reliability, safety, effectiveness, or performance of a drug, **combination product**, or device after it is released for distribution to market or clinic by either (1) Amgen or (2) distributors or partners for whom Amgen manufactures the material. **This includes all components distributed with the drug, such as packaging drug containers, delivery systems, labeling, and inserts.** This includes AMG 570/placebo provisioned and/or repackaged/modified by Amgen.

Any product complaint(s) associated with an investigational product supplied by Amgen are to be reported according to the instructions provided in the IPIM.

7.1.7 Excluded Treatments, Medical Devices, and/or Procedures During Study Period

Subjects who are receiving treatments listed below are allowed to remain in the study at the investigator's discretion. Subjects are also allowed to continue investigational product at the investigator's discretion except those who initiate any treatment listed below from a through i:

- a. investigational therapies or commercially available biologic agents **with immunosuppressive/immunomodulatory activity** for SLE or other conditions (eg, rituximab or belimumab)
- b. cytotoxic agents including: chlorambucil, cyclophosphamide, nitrogen mustard, or other alkylating agents
- c. **thalidomide**
- d. sirolimus
- e. oral calcineurin inhibitors (eg, tacrolimus, cyclosporine, etc.)
- f. T cell depleting agents (eg, antithymocyte globulin, Campath)
- g. recombinant IL-2 (eg, Proleukin)
- h. **JAK inhibitors**
- i. **live vaccines**
- j. intra-articular, **IM**, or **IV CS**, including adrenocorticotropic hormone
- k. intra-articular hyaluronic acid injections

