4.1 Objectives and Endpoints

Objectives	Endpoints
Primary	

 Evaluate the efficacy of AMG 570 at week 52 as measured by the Systemic Lupus Erythematosus (SLE) Responder Index (SRI-4) 	
 SRI-4 response at week 52
The primary estimand is the difference in SRI-4 response between each AMG 570 dose group and placebo at week 52 for all subjects with SLE with inadequate response to SOC therapy who are randomized regardless of investigational product discontinuation; subjects using more than protocol-allowed therapies will be considered as non-responders.	
Secondary	

 Evaluate the efficacy of AMG 570 at week 24 	
 SRI-4 response at week 24 British Isles Lupus Assessment Group (BILAG) based Combined Lupus Assessment (BICLA) response at week 24

 Evaluate the efficacy of AMG 570 at week 52 	
 Lupus Low Disease Activity State (LLDAS) response at week 52 BICLA response at week 52

 Evaluate the efficacy of AMG 570 as measured by SRI-4 response with oral corticosteroid (OCS)-tapering 	
 SRI-4 response at week 52 with reduction of OCS to \leq 7.5 mg/day by week 44 and sustained through week 52 in subjects with a baseline OCS dose \geq 10 mg/day

 Evaluate the efficacy of AMG 570 on disease flares 	
 Annualized moderate and severe flare rate (as measured by SELENA-SLEDAI Flare Index) over 52 weeks Annualized severe flare rate (as measured by SELENA-SLEDAI Flare Index) over 52 weeks Annualized flare rate (as measured by BILAG score designation of “worse” or “new” resulting in a B score in \geq 2 organs or an A score in \geq 1 organ) over 52 weeks

 Evaluate the efficacy of AMG 570 on joints and skin 	
 Total tender and swollen joint count (limited to hands and wrists): \geq 50% improvement from baseline at week

Objectives	Endpoints
	
12, 24, 36, and 52 in subjects with ≥ 6 tender and swollen joints in hands and wrists at baseline
 
 • Cutaneous Lupus Erythematosus Area and Severity Index (CLASI) activity score: $\geq 50\%$ improvement from baseline at week 12, 24, 36, and 52 in subjects with a CLASI activity score ≥ 8 at baseline

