Subjects will undergo a screening visit to confirm eligibility requirements. Baseline/day 1 visit should not occur prior to confirmation of subject's SLE-related eligibility by the adjudication team and must occur up to 33 days from the screening visit. At baseline/day 1 visit, prior to randomization, the subject must present with disease activity (defined by clinical hSLEDAI score ≥ 4) and stability and compliance with OCS and other immunosuppressant/immunomodulator doses (by reviewing medication history). Subjects may be randomized at any time after confirmation of all eligibility criteria, but the maximum time between initiation of screening and randomization is 33 days. Subjects who do not meet all the eligibility requirements at the baseline/day 1 visit will be considered screen failures. Subjects may be allowed to rescreen as detailed in Section 9.1.1.

After randomization, adjudication reviews will be completed throughout the study period on blinded endpoint data from enrollment to week 52 for all randomized subjects and for all visits. This includes review of all efficacy-related endpoint data.

Immunosuppressant/immunomodulator dose should remain stable through week 52. For OCS, initiation of, or temporary increases in OCS are allowed from weeks 0 to 8, provided that return to baseline dose occur within the subsequent 2 weeks, as outlined in Section 7.1.4.2. OCS can be tapered at the investigator's discretion but shall not be changed during the last 8 weeks (week 44 to 52) of the 52-week treatment period.

Subjects listed below will be allowed to continue the study but will be considered treatment failures for primary efficacy endpoint analyses for the subsequent time points. **These subjects will also be allowed to continue investigational product at the investigator's discretion, except subjects who initiate any immunosuppressant/immunomodulator listed in Section 7.1.7 (treatments a through i).**

- Subjects requiring initiation or increase in OCS dose > 5 mg/day (prednisone or equivalent), **or intramuscular (IM) CS or intravenous (IV) CS** at any time point during the study, subjects requiring initiation or increase in OCS dose ≤ 5 mg/day (prednisone or equivalent) after week 10, or subjects requiring initiation or increase in OCS dose ≤ 5 mg/day (prednisone or equivalent) from week 0 to week 8 who cannot return to their baseline dose within the following 2 weeks (Section 7.1.4.2).

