7.8.2 Concomitant Treatment

Throughout the study, investigators may prescribe any concomitant medications or treatments deemed necessary to provide adequate supportive care except for those listed in Section [7.1.7](#).

Concomitant therapies are to be collected from randomization through the end of the safety follow-up period. For concomitant therapies, collect therapy name, indication,

dose, unit, frequency, start date, and stop date. Guidelines for immunomodulators, immunosuppressants, and OCS are provided in Section 7.1.4.1 through Section 7.1.4.5.

8. Discontinuation Criteria

Subjects have the right to withdraw from investigational product and/or other protocol-required therapies, protocol procedures, or the study as a whole at any time and for any reason without prejudice to their future medical care by the physician or at the institution. The investigator and/or sponsor can decide to withdraw a subject(s) from investigational product, device, and/or other protocol-required therapies, protocol procedures, or the study as a whole at any time prior to study completion for the reasons listed in Sections 8.1, 8.2, and 8.2.1.

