9.2.2.11 Systemic Lupus Erythematosus Responder Index

The SRI-4 will be calculated as detailed in Luijten et al, 2012. **A subject achieves SRI-4 response if all of the following criteria are met:** ≥ 4 -point reduction from baseline in hSLEDAI score, AND no new BILAG **2004** A score and no > 1 new BILAG B domain scores compared with baseline (eg, **no B, C, D, or E scores at baseline becomes A or no more than 1 C, D, or E score at baseline becomes B**), AND no ≥ 0.3 -point deterioration from baseline in PGA VAS score (**scale 0 to 3**), AND **no use of more than protocol-allowed therapies (ie, initiation or increase in OCS dose > 5 mg/day prednisone [or equivalent] or IM CS or IV CS at any time point during the study; initiation or increase in OCS dose ≤ 5 mg/day prednisone [or equivalent] after week 10; initiation or increase in OCS dose ≤ 5 mg/day prednisone [or equivalent] between week 0 and week 8 that was not returned to baseline dose within the following 2 weeks; increase in current or initiation of new immunosuppressant/immunomodulator(s) at any time during the study)**. The latest visit date among hSLEDAI, BILAG, and PGA will be considered the SRI-4

visit date. In the case when all 3 visit dates are missing, the upper limit of the analytic window of this visit will be the SRI-4 visit date. When all 4 criteria are met, the subject is a responder at that time point according to the SRI-4 definition.

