2.1 Objectives and Endpoints/Estimands

Objectives	Endpoints
Primary	

 Evaluate the efficacy of rozibafusp alfa at week 52 as measured by the Systemic Lupus Erythematosus Responder Index (SRI-4) 	
 SRI-4 response at week 52
Primary Estimand	

The primary estimand is the difference in SRI-4 response rates between each rozibafusp alfa dose group and placebo at week 52 for all subjects with SLE with inadequate response to SOC therapy who are randomized, regardless of investigational product (IP) discontinuation; subjects will be considered non-responders for using more than protocol-allowed therapies as follows:
 
 initiation or increase from baseline in oral corticosteroid (OCS) dose > 5 mg/day (prednisone or equivalent) or intravenous (IV) or intramuscular (IM) at any time point during the study initiation or increase from baseline in OCS dose ≤ 5 mg/day (prednisone or equivalent) after week 10 initiation or increase from baseline in OCS dose ≤ 5 mg/day (prednisone or equivalent) between week 0 and week 8 that was not returned to baseline dose within the following 2 weeks initiation or increase from baseline of immunosuppressant/immunomodulator(s) at any time during the study 	
Secondary	

 Evaluate the efficacy of rozibafusp alfa at week 24 	
 SRI-4 response at week 24 British Isles Lupus Assessment Group (BILAG)-based Combined Lupus Assessment (BICLA) response at week 24

 Evaluate the efficacy of rozibafusp alfa at week 52 	
 Lupus Low Disease Activity State (LLDAS) at week 52

Objectives	Endpoints
	
 BICLA response at week 52

 Evaluate the efficacy of rozibafusp alfa as measured by SRI-4 response with oral corticosteroid (OCS)-tapering 	
 SRI-4 response at week 52 with reduction of OCS to \leq 7.5 mg/day by week 44 and sustained through week 52 in subjects with a baseline OCS dose \geq 10 mg/day

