Systemic Lupus Erythematosus Responder Index (SRI-4)

A subject achieves SRI-4 response if all of the following criteria are met:

1. ≥ 4 -point reduction from baseline in hSLEDAI score
2. no new BILAG 2004 A and no > 1 new BILAG 2004 B domain scores compared with baseline (e.g. no B, C, D or E scores at baseline becomes A or no more than 1 C, D or E score at baseline becomes B)
3. and < 0.3 -point deterioration from baseline in PGA (scale 0 to 3).
4. no use of more than protocol-allowed therapies (i.e. initiation or increase from baseline in oral corticosteroid (OCS) dose > 5 mg/day (prednisone or equivalent) or intravenous (IV) or intramuscular (IM) at any time point during the study; initiation or increase in OCS dose ≤ 5 mg/day (prednisone or equivalent) after week 10; initiation or increase in OCS dose ≤ 5 mg/day (prednisone or equivalent) between week 0 and week 8 that was not returned to baseline dose within the following 2 weeks; initiation or increase from baseline of immunosuppressant/immunomodulator(s) at any time during the study.)

The latest visit date among hSLEDAI, BILAG and PGA will be considered the SRI-4 visit date. In the case when all three visit dates are missing, the upper limit of the analytic window of this visit will be the SRI-4 visit date.

BILAG-based Composite Lupus Assessment (BICLA)

A subject achieves BICLA response if all of the following criteria are met:

1. at least one gradation of improvement in baseline BILAG domain scores in all body systems with moderate or severe disease activity at entry (e.g., all A (severe disease) domain scores at baseline falling to B (moderate), C (mild), or D (no activity), and all B domain scores at baseline falling to C or D)
2. no new BILAG 2004 A domain score and no > 1 new BILAG 2004 B domain scores compared with baseline
3. no worsening of the hSLEDAI score from baseline
4. < 0.3-point deterioration from baseline in PGA (scale 0 to 3)

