5. and no use of more than protocol-allowed therapies (i.e. initiation or increase from baseline in oral corticosteroid (OCS) dose > 5 mg/day (prednisone or equivalent) or intravenous (IV) or intramuscular (IM) at any time point during the study; initiation or increase in OCS dose ≤ 5 mg/day (prednisone or equivalent) after week 10; initiation or increase in OCS dose ≤ 5 mg/day (prednisone or equivalent) between week 0 and week 8 that was not returned to baseline dose within the following 2 weeks; initiation **or increase from baseline** of immunosuppressant/immunomodulator(s) at any time during the study.

Swollen and Tender Joint Count

Joints that have been replaced during the study, or have suffered trauma or received intra-articular injections, are considered non-evaluable.

Swollen Joint Count Assessments – A total 28 joints will be scored for presence or absence of swelling. A separated score for joints in the hands and wrists will be calculated.

Tender Joint Count Assessments – A total 28 joints will be scored for presence or absence of tenderness. A separated score for joints in the hands and wrists will be calculated.

Swollen and Tender Joint Count Assessments: joints in hands and wrists will be scored for the simultaneous presence of absence of swelling and tenderness.

Cutaneous Lupus Erythematosus Area and Severity Index (CLASI)

The CLASI consists of 2 scores, the first summarizes the activity of the disease while the second is a measure of the damage done by the disease. Activity is scored based on erythema, scale/hyperkeratosis, mucous membrane involvement, acute hair loss and non-scarring alopecia. Damage is scored in terms of dyspigmentation and scarring, including scarring alopecia. Subjects are asked whether dyspigmentation due to cutaneous lupus lesion usually remains visible for more than 12 months, which is taken to be permanent. If so, the dyspigmentation score is doubled. The scores are calculated by simple addition based on the extent of the symptoms. The CLASI is designed as a table where the rows denote anatomical areas, while the columns score major clinical symptoms. The extent of involvement for each of the skin symptoms is documented according to specific anatomic areas that are scored according to the worst affected lesion within that area for each symptom.

A CLASI response is defined as $\geq 50\%$ improvement of CLASI activity score from baseline.

Lupus Low Disease Activity State (LLDAS)

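### Intra-articular steroid is excluded during the study but missing from the SRI-4 failure lists, and the hSLEDAI arthritis item has no rule for an injected joint

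*Protocol*

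**What the plan says.** **Exclusion.** Protocol 7.1.7 item j lists "intra-articular, IM, or IV CS, including adrenocorticotropic hormone" among the excluded treatments. Only items a to i require investigational product to stop, and the section gives no responder status for any item. Protocol 7.8.2 says "investigators may prescribe any concomitant medications or treatments deemed necessary to provide adequate supportive care except for those listed in Section" 7.1.7.

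**Estimand.** Protocol 4.1: "subjects using more than protocol-allowed therapies will be considered as non-responders". SAP 2.1 opens its list with "subjects will be considered non-responders for using more than protocol-allowed therapies as follows".

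**Failure lists.** Beyond oral dose changes and immunosuppressants/immunomodulators, the steroid wording is:
- Protocol 5.1: "or intramuscular (IM) CS or intravenous (IV) CS"
- Protocol 9.2.2.11, SRI-4: "or IM CS or IV CS at any time point during the study"
- SAP 2.1, and SAP 5.6 under SRI-4 criterion 4: "or intravenous (IV) or intramuscular (IM) at any time point during the study"
- SAP 5.6, BICLA criterion 5: begins "and no use of more than protocol-allowed therapies (i.e. initiation or increase from baseline in oral corticosteroid (OCS) dose" and goes on to the same IV and IM routes

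**Joints.** Protocol 9.2.2.5 and the joint-count part of SAP 5.6 make an injected joint non-evaluable. SAP 8.3 prorates joint counts when joints are excluded. The hSLEDAI arthritis item (SAP Appendix B) scores 4 when more than two hand/wrist joints are inflamed. Protocol 6.1 (criterion 104) and 9.2.2.1 put this as at least three joints. None of the hSLEDAI text mentions an injected joint.

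**The concern.** Two gaps lead to the same endpoint. First, a therapy that the protocol excludes does not trigger the non-response that the estimand attaches to excess therapy, although two other routes on the same line of 7.1.7 do. Second, the injection acts directly on a scored item. A hand or wrist joint quieted by local steroid can reduce the arthritis item, and the rule that sets such a joint aside applies to the joint counts and not to the index that drives SRI-4. At stake is whether some SRI-4 responses reflect a local injection and not the randomized treatment, and whether two people scoring the same record could classify a subject differently.

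**Working it through.** The plan gives no figure for this point, so the check sets the texts side by side and then bounds the size.

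**1. The lists**

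| Place | Form | Steroid routes | Catch-all clause |
|---|---|---|---|
| Protocol 5.1 | bulleted failure list | oral, IM, IV | none |
| Protocol 9.2.2.11 (SRI-4) | closed (*ie*) | oral, IM, IV | none |
| SAP 2.1 (estimand) | closed (*as follows*) | oral, IV, IM | none |
| SAP 5.6 (SRI-4) | closed (*i.e.*) | oral, IV, IM | none |
| Protocol 9.2.2.12 (BICLA) | closed (*ie*) | oral, IM, IV | yes, for SLE treatment outside the protocol |
| SAP 5.6 (BICLA) | closed (*i.e.*) | oral, IV, IM | none |

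**2. Text that might close the gap**
- Protocol 7.1.4.1: the immunosuppressant limb carves out corticosteroids.
- Protocol 7.1.4.2: fails a steroid start or increase after week 10 without naming a route. However, its heading is limited to oral, IM and IV, and the routeless wording is not carried into the SRI-4 definition or the SAP.
- Protocol 9.2.2.5 and SAP 8.3: joint counts only.

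**3. The arthritis item with one injected joint**

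Let *a* be the number of active hand/wrist joints other than the injected one.
- *a* ≥ 3: the item is 4 whatever the injected joint shows.
- *a* ≤ 1: the item is 0, since at most 2 joints can be active.
- *a* = 2: the injected joint decides. If it was active at baseline, 3 joints gave 4 points. If it is now quiet or dropped, 2 joints give 0. The change is 0 − 4 = −4, which equals the SRI-4 hSLEDAI threshold.

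To score as inactive in its own right, the joint must be quiet over the 30-day look-back (Protocol 9.2.2.1). The BILAG and PGA criteria must also be met.

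If the item is instead treated as missing, SAP 8.3 carries forward the previous post-baseline value. Baseline is never carried, and a total that cannot be evaluated counts as not meeting the reduction. That protects the endpoint, but only if someone decides that the item is missing.

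**4. Size**

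Inputs: 320/4 = 80 per planned arm; response 40% on placebo and 40 + 25 = 65% on active (Protocol 10.1). The documents give no injection rate, so r = 1% to 5% is an assumption, with injected subjects responding at the design rates.
- One subject: 1/80 = 1.25 points. At the sixth interim the placebo group was at least about 0.25 × 200 = 50, because the interim set also takes subjects who had reached only week 16 (SAP 6.4), and was under 80. One subject there is therefore 1.25 to 2.0 points.
- Placebo subjects changing status: 80 × r × 0.40 = 0.32 to 1.6, or 0.4 to 2.0 points.
- Active subjects changing status: 80 × r × 0.65 = 0.52 to 2.6, or 0.65 to 3.25 points.
- Equal r in both arms: the difference shrinks by r × 25 = 0.25 to 1.25 points.
- Injections on placebo only would widen the difference by 0.4 to 2.0 points. Injections on active only would narrow it by 0.65 to 3.25.
- For scale, SE = √(0.65 × 0.35/80 + 0.40 × 0.60/80) = 7.6 points.

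**The case against.** The strongest reply is that there is no ambiguity in SRI-4 itself. Several lists agree and most are closed, so they are the definition, and under it intra-articular steroid is not failure. That stands.

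The omission may also be deliberate. The summary of Amendment 3 records that it clarified the steroid types in 7.1.4.2 and the events that make a joint non-evaluable. That would fit a split in which systemic steroid fails the subject and local steroid sets aside the joint. Topical steroid, NSAIDs and anti-proteinuria agents (7.1.4.3 to 7.1.4.5) carry no failure rule. A reader might infer from the shared line in 7.1.7 that failure was intended for all three routes, but the documents do not support this: live vaccines and hyaluronic acid injections are on the same list and on no failure list. The same summary says that the Important Protocol Deviation list now defines excess therapy. That list is not supplied and may already name the route.

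On scoring, SAP 8.3 counts non-evaluability of a measurement as a cause of missing data, so the LOCF rule could be applied. Efficacy data are also adjudicated (SAP 9.5). Both points have weight, but the adjudicator works to instrument specifications that do not mention an injected joint, and nothing says that the item becomes missing.

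A reader might also expect proration to hold the item at 4, because 2 × 22/21 = 2.10 exceeds 2. It would not: 2.10 falls short of the three joints that the protocol requires, and proration is written for joint counts.

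**Conclusion.** The point holds as a modest one. The SRI-4 rule is clear, but it leaves an excluded and directly acting therapy outside the failure definition with no stated reason, and the arthritis item lacks a rule in the one configuration where the injected joint decides it. SAP BICLA has also lost the protocol clause that could have caught an injection given for lupus.

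The likely effect is small: at most a few subjects per arm under the assumed 1% to 5%, and a shift in the difference well inside its standard error. The direction depends on which arms had injections, and the documents do not show this. The scoring problem alone touches fewer subjects than these counts, which cover every injected responder.

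A reader might infer that the futility stop or the adaptive randomization was distorted. The documents give no basis for that. Those decisions are complete, and SAP section 10 replaces treatment comparisons with descriptive statistics. What remains open is how the descriptive response tables are read and whether the definition is reused.

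**What to change.** - **Main summary:** keep SRI-4 and BICLA as pre-specified.
- **SAP 9.5:** add a supplementary summary in which intra-articular steroid into a hand/wrist joint, or given for SLE activity, counts as excess therapy. Report the number changing status by arm. Label it as added after the futility decision, since SAP 7.1 lifts the blinding commitment once futility is determined.
- **SAP 8.3:** state that when an injected joint decides the arthritis item, the item is missing and goes through the existing LOCF/not-met rule.
- **SAP 5.6, BICLA:** restore the closing clause of Protocol 9.2.2.12 on SLE treatment outside the protocol.
- **Deviation list:** if it already covers this route, carry its wording into the SAP.
- **Future use:** add the route to the failure list.

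**Cost:** one concomitant-medication flag, one descriptive table and a few sentences. Therapy name and indication are collected (Protocol 7.8.2). Route is not a listed field there, but the IM/IV rule already needs it. The injected joint is not listed either, though the joint-count record of non-evaluable joints may show it. Response rates in the supplementary table may be slightly lower, and some subjects injected in the hand or wrist for reasons other than SLE will count there as non-responders.
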